This is a phase 4 open label feasibility study of extended release naltrexone (Vivitrol, Alkermes Pharmaceutical), case management and tele-addiction medicine for treatment of alcohol use disorders in the ED. The planned study period is 2 years. During this time we will conduct necessary department staff training and recruit 25 patients. Each patient will be followed for 12 months from index visit by our study staff, with case management provided by a full-time research case manager. Patients will be enrolled consecutively, 24 hours a day, 7 days a week. Recruitment will take place in the UCSF Emergency Department, Parnassus campus. Follow up visits may occur in the UCSF ED or an outpatient setting agreed upon by the patient and the research case manager. Patients who drop out of the study will be replaced with new patients; enrollment will end once 25 patients have been retained in the study or at the planned end date.

Initial Screening:

All adult patients presenting to the University of California San Francisco ED during the study period will be screened for frequent ED utilization (defined as 3 or more ED visits in the past 12 months including the index visit) by electronic medical record review conducted by the treating physician or member of the research team. UCSF, San Francisco General, and several other academic and community emergency departments in the San Francisco Bay Area share an electronic platform called the Emergency Department Information Exchange, or EDIE, that documents dates of ED visits and diagnoses. UC emergency providers can view visits at each of these sites, and ED visits to any hospital will be counted towards this 3-or-more threshold.

Determination of Eligibility:

An ED provider or staff (including physicians, advanced health practitioners, nurses, social workers, and case managers) may alert the PI or research study staff of potentially eligible patients based on the initial screen. The research team member will then determine eligibility as described below.

The PI [name], research fellow [name] or study staff (the research case manager) can all determine study eligibility. Initial eligibility will be determined based on chart review during the time of an ED visit. During study hours, the above mentioned faculty and staff will examine the

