Patients identified as frequent ED users will undergo an alcohol use disorder screening conducted by the research case manager, PI, or research fellow using a validated screening tool, the Alcohol Use Disorder Identification Test (AUDIT) which constitutes the screening component of SBIRT. The AUDIT places patients into one of four categories: low risk, risky, harmful, and severe. Brief intervention and pharmacotherapy have previously been shown to be most effective in those with harmful or severe use disorders [12]. Patients found to have at least harmful alcohol use based on the screening will be offered enrollment (AUDIT score ≥ 8). Enrollees will have blood and urine samples collected to screen for active opiate use including fentanyl, platelet counts, pregnancy, or significant liver disease (see exclusion criteria below) if no results are available in EHR. With the exception of urine pregnancy screening these tests are done as part of the routine care of emergency department patients with alcohol use disorders who are interested in accessing treatment. The results will be used to confirm inclusion/exclusion criteria are met. Patients meeting all criteria will be enrolled into the study and will receive 380mg of extended-release naltrexone as an intramuscular injection in the ED.

Naltrexone training and administration:

Study staff will compose and send e-mail before the start of the study, with input from UCSF ED nursing leadership, to all ED RNs informing of the intent and responsibilities of the study. Subsequently, during RN sign out (twice daily at 7am and 7pm) study staff will remind ED RNs about the study protocol to ensure as much staff as possible is aware of RN involvement and responsibilities. The shift-change information session will be performed for a two week run in period to assure all RNs are oriented.

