The medical bracelet or wallet card will alert providers that opiate dosing adjustments may be necessary to adequately treat acute pain should the patient require treatment during the study period. It will provide information about the added precautions necessary should that patient require opioid pain management. Specifically, as the amount of opioid required to achieve adequate analgesia may be increased any resulting respiratory depression may be deeper and more prolonged. Therefore a fast acting agent is preferred and the amount of opioid analgesic should be titrated to the clinical effect in a setting equipped for cardiopulmonary resuscitation. The PI will be available by phone for emergency consultation at any time.

Visit 2-3 study procedures:

Patients will receive a monthly intramuscular injection of extended release naltrexone for up to 3 consecutive months during visits for which the research case manager will outreach to the participants in the community. Injections will be administered in an outpatient setting by an addiction community provider familiar with XR-Naltrexone, or in the UCSF ED depending on patient preference. A 20-dollar gift card incentive will be used to encourage follow-up at the time of each injection. We will follow participants for 12 months from the time of enrollment (an additional 9 months after the final dose of XR-NTX administered on behalf of the study). Specimens for alcohol biomarker testing will be collected at follow up visits.

At each of the monthly follow up visits we will collect data on a) feasibility measures and b) study outcomes. During the follow-up period, the research case manager will track all participants and we will continue to collect data on study outcomes using REDCap including ED and inpatient hospital use, substance use, readiness to change, and engagement in substance use recovery/rehabilitation via community treatment programs, as well as subsequent doses of XR-Naltrexone administered. This data will be collected by administering the same validated questionnaires used in the index visit (AUDIT, ASI, SIP-2R). The PI and research fellow will also query the EDIE system and UCSF EHR monthly in order to identify any emergency department visits that could be related to the study procedures.

Follow up procedures after visit 3:

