Patients who miss scheduled follow up injection visits will be contacted and asked to reschedule their injection visit as soon as possible. If they are able to reschedule within 2 weeks then no changes to study procedure are necessary. If they are able to reschedule within 2-4 weeks then they will be asked if they have used any opiates (including fentanyl) in the past 7 days. If they have not used opiates in the past 7 days then they will resume treatment, provided they are not endorsing any signs or symptoms of liver injury. If they endorse signs or symptoms of liver injury they will undergo screening as outlined above. If they endorse using opiates then they will not be allowed to resume treatment through the study. If a patient is unable to reschedule a missed injection appointment within one month they will not be allowed to continue in the study. If a patient is unable to resume treatment through the study then they will be provided with alternative follow up options (see transition to ongoing care).

Participant Payment:

A 20-dollar gift card incentive will be used to encourage attendance at the 6 monthly follow up visits required for XR-Naltrexone injections. Gift cards will be given at each of the six visits. The total value of gift cards available to each participant during the study period is \$120.00. Gift cards will be issued for locations that do not sell alcohol (e.g. Starbucks coffee).

Study Subjects:

The target population is patients with frequent ED visits for alcohol related complaints who may benefit from ED-initiated XR-NTX. The accessible population is all people in the San Francisco Bay Area presenting to the ED with an alcohol related complaint. The study sample will be adult

patients presenting to the UCSF ED with active hazardous or high risk alcohol use and ≥ 4 ED visits in the past 12 months for alcohol related complaints.

Inclusion Criteria:

- Age ≥ 21
- AUDIT score ≥ 8
- Frequent emergency department visits, defined as: At least 3 emergency department visits for in the past 12 months, including the index visit.

Exclusion Criteria:

- Opioid use: currently receiving opioid analgesics, self-report of opioid use in past 7 days, current physiologic opioid dependence, patients in acute opioid withdrawal, urine toxicology screen positive for opiates including fentanyl
- History of hypersensitivity to naltrexone, polylactide-co-glycolide (PLG), carboxymethylcellulose, or any other components of the diluent

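### The missed-injection rule removes patients from the study, not only from treatment, and nothing in the plan secures their 12-month ED-visit data or their place in the intention-to-treat set

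*Combined protocol and SAP*

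**What the plan says.** Section II, Handling of missed injection visits, contains two kinds of exit. For a patient who reports opiate use on late rescheduling: "If they endorse using opiates then they will not be allowed to resume treatment through the study". For a patient who cannot rebook in time: "If a patient is unable to reschedule a missed injection appointment within one month they will not be allowed to continue in the study". The paragraph closes on treatment again: "If a patient is unable to resume treatment through the study then they will be provided with alternative follow up options", with a pointer to Transition to ongoing care.

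Elsewhere the plan describes complete follow-up. Overview of Design: "Each patient will be followed for 12 months from index visit by our study staff". Visit 2-3 study procedures: "During the follow-up period, the research case manager will track all participants and we will continue to collect data on study outcomes". Follow up procedures after visit 3 adds a final analyst review of the EHR and EDIE at 12 months. Section IV defines the pilot primary outcome as alcohol-related ED visits in the 12 months after enrolment minus those in the 12 months before. It also plans intention-to-treat and per-protocol analyses, and defines neither population.

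On replacement, Overview of Design replaces drop-outs and says "enrollment will end once 25 patients have been retained in the study or at the planned end date". Section IV, Sample Size, also replaces drop-outs, whom it describes as withdrawn or lost to follow-up, but it stops at 25 recruited and mentions no end date.

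**The concern.** Leaving treatment and leaving the study have different consequences for the data. If a patient stops injections but stays in the study, the 12-month ED count can still be read from records. If the patient is out of the study, staff may reasonably stop collecting data and enrol a replacement.

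The patients affected are those who did not adhere, so the remaining group would be selected by something that happened after treatment began. A before/after comparison in that group describes completers and is not an intention-to-treat result. The retention figures, which are among the primary feasibility outcomes, would also depend on whether removed and replaced patients stay in the denominator. The plan itself expects significant drop-out, and its timeline has the results leading into a proposal for a randomised trial, so both quantities will be used.

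**Working it through.** **The plan's own figure.** Sample Size gives N = 25 and a standardized effect of 0.584 for a paired t test. Assuming two-sided 5% and 80% power (neither is stated), the noncentral t calculation gives a detectable effect of 0.5840 at n = 25, and power of 0.800 at 0.584. In visits, 0.584 × 3.5 = 2.04 and 0.584 × 8.58 = 5.01, which match the stated 2 to 5. The figure reproduces. It presupposes 25 complete before/after pairs, so it matters who supplies those pairs.

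**The passages side by side.**

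- *Missed-injection rule against follow-up.* A patient not allowed to continue in the study cannot also be followed by study staff for 12 months, unless study here means the injection phase. The text does not say that it does.
- *Where the removed patient is sent.* Transition to ongoing care covers patients who have completed three injections or have dropped out. A patient removed for a missed injection has not completed three, so only the drop-out branch fits. Drop-outs are replaced.
- *Whether removal is drop-out.* Sample Size names withdrawal and loss to follow-up. Removal by the study team is neither, so it is unstated whether such a patient is replaced.
- *Final record review.* It is not limited to completers, but it does not say that removed or replaced patients are included. The monthly telephone follow-up is described only for the 9 months after the final injection visit.
- *Stopping rule.* One section ends enrolment at 25 retained or the planned end date. The other stops replacement at 25 recruited. Taken literally, the second is met at the 25th enrolment, whoever has dropped out.

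**Outcome time lost per removed patient, on the literal reading.** Visit 2-3 study procedures sets the schedule: "Patients will receive a monthly intramuscular injection of extended release naltrexone for up to 3 consecutive months". With injections at months 0, 1 and 2, and removal one month after an injection that is missed and not rebooked:

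| Pattern | Removed at about | Months lost of 12 |
|---|---|---|
| Second injection missed | 1 + 1 = month 2 | 12 − 2 = 10 |
| Third injection missed | 2 + 1 = month 3 | 12 − 3 = 9 |
| Second given one month late (month 2), third then due at month 3 and missed | 3 + 1 = month 4 | 12 − 4 = 8 |

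Participant Payment refers to six monthly injection visits. If that schedule applied, removal could come later and fewer months would be lost.

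**Patients outside a retained-25 set.** The documents give no drop-out rate, so d below is an assumption. Enrolments needed to retain 25 = 25 / (1 − d), rounded up.

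- d = 30%: 25 / 0.70 = 35.7, so 36 enrolled and 36 − 25 = 11 outside.
- d = 50%: 25 / 0.50 = 50 enrolled and 50 − 25 = 25 outside.

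These counts cover all drop-outs. The share due to the missed-injection rule is unknown.

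**The case against.** The strongest reply is that the rule concerns treatment only. It sits under a heading about injection visits, the closing sentence speaks of being unable to resume treatment, and the plan uses the word study loosely: section IV refers to a 3-month study period, while section II refers to a 12-month one. On that reading the follow-up and intention-to-treat statements stand without contradiction. In addition, ED counts come from records, the final review has no completer restriction, and intention to treat ordinarily means everyone enrolled. Replacement is openly justified, and the plan acknowledges substantial risk of bias. The consent form, which is not in our copy, may already permit continued record access.

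Much of this stands. The treatment-only reading is plausible, and an intention-to-treat analysis of ED visits remains possible. But no passage secures that reading, states that removed or replaced patients' records are still reviewed, or says who is in the intention-to-treat set.

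A reader might go further and infer that removed patients' visits would be counted only up to removal, producing an artificial fall, or that retention would be reported as 100% of the final 25. The documents support neither. The outcome is defined over 12 months, and no passage proposes a shortened count or a completers-only denominator.

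**Conclusion.** The point holds as a gap in the wording with real consequences if the rule is followed literally. The missed-injection rule, the replacement rule and the undefined intention-to-treat set together allow the ED-visit change and the retention results to rest on patients selected after treatment.

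The loss of about 8 to 10 of 12 outcome months per removed patient depends on the literal reading and on three monthly injections. The 11 to 25 patients outside a retained-25 analysis depend on an assumed 30-50% drop-out. A reader might infer that the results would necessarily look too favourable. The documents do not allow that conclusion, because they give neither a drop-out rate nor any information on how ED use differs between those who leave and those who stay. Severity is minor to moderate. It is worth fixing mainly because the fix costs so little.

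**What to change.** 1. Reconcile Handling of missed injection visits with Overview of Design, Visit 2-3 study procedures and Follow up procedures after visit 3. State that ending study injections, or being replaced, does not end EHR/EDIE collection of ED visits to 12 months unless the patient withdraws consent for data use. Check this against the consent form. The rule on resuming treatment is left unchanged.
2. In section IV, define the intention-to-treat set, and the denominator for retention, follow-up and doses received, as every enrolled patient, including those replaced or removed. The Enrollment section already supplies the definition: "Patients meeting all criteria will be enrolled into the study". Report the number replaced or removed.
3. Use one stopping rule in Overview of Design and Sample Size, and say whether removal after a missed injection counts as drop-out for replacement.

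The cost is a few sentences, plus a few more record queries within a final review that is already planned. The retention figure may be less favourable. Questionnaire and biomarker outcomes still need patient contact, and this change does not recover them.

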ED trackboard to determine if any patients currently in the ED at UCSF have made at least 4 ED visits in the past 12 months to UCSF or a combination of UCSF, ZSFG, or other hospitals based on shared data in our emergency department information exchange platform. If an individual is determined to be eligible based on these criteria, the faculty or study staff will review the chart for the most recent lab results including liver function tests (AST, ALT), platelets, and urine or serum pregnancy tests and urine toxicology testing specifically the presence of opioids including fentanyl (see exclusion criteria for specific cut off values). They will also review the past medical history and allergies in the electronic medical record to determine if the patient has cirrhosis or a document allergy to naltrexone or inactive ingredients contained in naltrexone XR. When a patient is determined to meet criteria inclusion by electronic record review, a study staff member will discuss the case with the ED provider caring for the patient to confirm the patient is willing to be approached, is clinically sober, and medically stable. The ED provider will then introduce the patient to the research staff who will discuss the study with the patient. The research staff member will assess the patient's willingness to participate. If a patient expresses interest in participating the research staff member will confirm the accuracy of information obtained from the medical record review that pertains to inclusion and exclusion criteria. If no discrepancies are found the research team member describe the study in detail and will perform a capacity assessment using the University of California San Diego Brief Assessment of Capacity to Consent to Research (UBACC) if there are any concerns about the participant's capacity to consent, such as ongoing alcohol or drug intoxication or withdrawal.

Capacity Assessment:

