The risk of bias is substantial given that all enrollees are to be treated with XR-NRT and the study is not randomized or blinded and the population of interest is at high risk of being lost to follow up. We intend to conduct both an intention to treat analysis and a per protocol analysis, though our sample size may limit the utility of this approach. We will employ an independent data analyst to collect the ED visit counts and perform the final statistical analysis.

Statistical issues:

Statistical Test: Paired T Test

Hypothesis:

ED initiated Treatment of alcohol use disorders with multi-modal therapy reduces alcohol related ED visits in patients with frequent ED visits for alcohol related complaints

Sample Size:

We will enroll 25 patients. As a feasibility study our sample size was chosen as it represents a reasonable patient load for a single case manager. Because this population is difficult to retain in treatment, we anticipate the drop-out rate will be significant. Patients who drop out of the study (either withdraw or are lost to follow up) will be replaced with new enrollees until 25 patients have been recruited into the study. The goal of this practice is to maximize the benefit to the patient population, avoid wasting donated study medication, and to allow the research team to optimize recruitment and retention strategies.

Last year 42 patients presented to the UCSF Emergency Department at least 4 times for an alcohol related complaint. Of this group the mean number of visits was 8.49 with a SD of 8.58. The median number of visits was 6. The number of visits ranged from 4-47. After excluding 2 outliers (40 and 47 visits, each $> 3SD$ above the mean) the mean was 6.78 visits with a SD of 3.5 visits.

We estimate a standardized effect size of 0.584 would represent 2-5 emergency visits for alcohol related complaints. This equates to a 29-59% reduction in ED utilization, which is clinically relevant.

Data management plan:

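### The entry rules count ED visits of any cause, while the described sample, the ED-visit outcome, the hypothesis and the planning figures concern alcohol-related visits only

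*Combined protocol and SAP*

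**What the plan says.** Three places in section II of the protocol set the visit count for entry, and none names a reason for the visits.

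- Initial Screening: frequent use is "defined as 3 or more ED visits in the past 12 months including the index visit", and "ED visits to any hospital will be counted towards this 3-or-more threshold".
- Determination of Eligibility: staff look on the trackboard for patients who "have made at least 4 ED visits in the past 12 months to UCSF or a combination of UCSF, ZSFG, or other hospitals".
- Inclusion Criteria: "At least 3 emergency department visits for in the past 12 months, including the index visit". Something seems to have dropped out after the word for.

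The only alcohol item in the inclusion list is an AUDIT score of at least 8.

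Elsewhere the visits are alcohol-related. Study Subjects, directly above the inclusion list, describes a sample with "≥ 4 ED visits in the past 12 months for alcohol related complaints" and an accessible population that comes to the ED with such a complaint. In section IV, the primary outcome of the pilot analysis is the alcohol-related visit count in the 12 months after enrollment minus the count in the 12 months before. The hypothesis is that treatment "reduces alcohol related ED visits in patients with frequent ED visits for alcohol related complaints". The planning data under Sample Size come from a matching group: "Last year 42 patients presented to the UCSF Emergency Department at least 4 times for an alcohol related complaint".

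**The concern.** Staff enroll from the screening steps and the inclusion list. AUDIT measures drinking, not why someone came to the ED. If the visit count carries no reason, a patient can qualify with no alcohol-related visit in the year before enrollment. The ED-visit outcome cannot fall for that patient.

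Two things are at stake. The before/after estimate would mix patients whom the hypothesis names with patients whom it does not. The planning means, standard deviations and target reduction would also describe a different group from the one enrolled. Section VI says that a randomized trial proposal is to follow, so a visit estimate from an unclear population could carry over into that design.

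**Working it through.** **Passages side by side**

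| Place in protocol | Number of visits | Reason for visit |
|---|---|---|
| Initial Screening | 3 or more | none stated |
| Determination of Eligibility | at least 4 | none stated |
| Inclusion Criteria | at least 3 | none stated (words apparently missing) |
| Study Subjects | at least 4 | alcohol-related |
| Primary outcome, section IV | not applicable | alcohol-related |
| Hypothesis | frequent, no number | alcohol-related |
| Planning set, Sample Size | at least 4 (range 4 to 47) | alcohol-related |

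**One patient through the steps.** Take a 21-year-old with an AUDIT score of 8, three ED visits for asthma in the year and no exclusion. This patient meets Initial Screening and every item of the inclusion list. With a fourth such visit, the patient also meets the trackboard check. The chart review that follows covers liver tests, platelets, pregnancy, toxicology, cirrhosis and allergy. It does not cover the reason for earlier visits.

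**The change score.** Change = after − before. If before = 0, then change = after, which is at least 0.

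**The plan's own figures.** The inputs, all from Sample Size, are effect size 0.584; N = 25; mean 8.49 and SD 8.58 for all 42 patients; and mean 6.78 and SD 3.5 after two outliers are removed. The plan states no significance level, sidedness or power. Assuming a two-sided 5% level and 80% power, the exact noncentral-t calculation for a paired t test with N = 25 gives a detectable effect of 0.584. The rest follows:

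- 0.584 × 3.5 = 2.04 visits, and 0.584 × 8.58 = 5.01 visits (the plan's 2 to 5)
- 2 / 6.78 = 29.5%, and 5 / 8.49 = 58.9% (the plan's 29 to 59%)

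All of these rest on patients with at least 4 alcohol-related visits.

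**Illustration of dilution.** Let q be the share of entrants with no earlier alcohol-related visit. The documents do not give q. Set the change of these patients to 0, the most favorable value it can take. Let the others have a mean reduction of 0.584σ with SD σ. Then

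- mean reduction = (1 − q) × 0.584σ
- variance = (1 − q)σ² + q(1 − q)(0.584σ)²
- d = (1 − q) × 0.584 / √[(1 − q) + q(1 − q) × 0.341], since 0.584² = 0.341 and σ cancels

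For q = 20%: d = 0.467 / √(0.8 + 0.16 × 0.341) = 0.467 / 0.924 = 0.505. Power at N = 25 is 68%.

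For q = 40%: d = 0.350 / √(0.6 + 0.24 × 0.341) = 0.350 / 0.826 = 0.424. Power at N = 25 is 53%.

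A simulation of the same mixture, with normally distributed changes in the other patients, gives 69% and 54%.

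**The case against.** The strongest reply is that this is a drafting slip. The inclusion bullet is visibly incomplete, the loss may even come from reading the PDF, and Study Subjects states the intended sample. That stands as far as the bullet goes. A reader might infer that nothing in the protocol requires alcohol-related visits. The documents do not support that, because Study Subjects does require them. But the sentences in Initial Screening and Determination of Eligibility are complete and carry no such condition, so repairing the bullet alone would leave the conflict in place.

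A second reply is that the broad screen may be deliberate. Section I proposes a feasibility pilot in people with alcohol use disorder who use the ED often, and frequent visits plus AUDIT fit that aim. This is fair, and the fix allows for it. It does not make the hypothesis or the planning set apply to such patients.

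A third reply is that little depends on the ED-visit analysis. Section IV puts the feasibility measures first and says that the study cannot estimate efficacy or cost precisely. N = 25 was set by the case manager's workload. This stands, and it lowers the weight of the point.

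Two stronger readings of the numbers are tempting. One is that an expected reduction of 2 to 5 visits would shrink in proportion to q. The plan's 2 to 5 is 0.584 multiplied by two alternative SDs, not a predicted mean reduction, so it cannot be read that way. The other is that the cost per avoided ED visit is distorted in the same way. Section IV does not limit that measure to alcohol-related visits, so this is not shown.

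**Conclusion.** The contradiction is real and holds whichever visit number is chosen. As written, the screening steps and the inclusion list admit patients whom Study Subjects and the hypothesis leave out. For those with no earlier alcohol-related visit, the change score cannot be negative and the planning figures do not apply.

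The direction of the effect on the ED-visit analysis is certain, but its size is not. The fall in power from 80% to about 68% or 53% rests on assumed shares of 20% and 40%, an assumed two-sided 5% level, and zero change in those patients. It illustrates sensitivity and does not forecast the result. The feasibility outcomes are largely unaffected. This should be fixed, but it does not undermine the study's main purpose.

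**What to change.** Reconcile Initial Screening, Determination of Eligibility and Inclusion Criteria with Study Subjects, so that the entry count is ED visits for an alcohol-related complaint. Settle the conflict between 3 and 4 visits in the same edit. Define an alcohol-related complaint once, since the documents do not, and use that definition for both entry and outcome. According to Initial Screening, the shared ED platform already shows diagnoses, so the rule can be applied during the chart review already planned.

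If frequent users of any cause are wanted for the feasibility aims, say so. In that case keep the ED-visit analysis on all enrolled patients, which respects the planned intention-to-treat analysis. Add a labelled analysis of those who meet the alcohol-related count, and state that the planning figures apply only to that subgroup.

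The amendment involves more than wording, because the definition has to be written. It also has two costs that the plan should state.

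- **A smaller pool.** The plan reports 42 patients in a year with at least 4 such visits at UCSF, so enrolling 25 would take 25 / 42 = 60% of a year's group, before exclusions, refusals and replacement of drop-outs. Counting visits at other hospitals could enlarge the pool.
- **More regression to the mean.** When entry depends on a high earlier count of the outcome itself, a single-arm before/after comparison tends to show a fall even without a treatment effect. The labelled subgroup analysis has the same weakness. The report should say that such a fall cannot be credited to treatment alone.
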